#### E.2. Procedures

1. Summarize the research design and sequentially identify all procedures to be performed to accomplish the specific aims of the project.: Participants meeting the eligibility criteria will be randomly assigned to one of two randomization sequences (Phase I and Phase II), the meat or plant-based meat alternative entrées, or vis versa, to achieve a crossover design. There will be a 2-week washout period between the phases.

During each diet phase, participants will be provided with 2 study entrées per day and counseled by the research dietitian to consume them at two different times during the day. The length of each diet phase will be ~3 weeks (i) 2 weeks of meat or plant-based meat alternative entrées, (ii) ingestion of the mini-pills on week 2 (day 14), and week 5 (day 49) of the diet phases, and (iii) additional 2 to up to 6 days (consuming 2 entrées/day) until the mini-pills are recovered from the stool. In humans, prior work has established the adequacy of the intervention period to affect microbial communities. A prior study in humans using a similar device indicated that all devices were recovered in stool using a collection window between 6 and 48 hours. The mini-pill recovery window in our study using pigs and hounds was up to 72 hours. We plan to use the appearance of blue dye in the stool to better tailor the stool collection window for our participants.

Table 1: Summar	v of Study	Timeline and	l Procedures
Table 1. Sallilla	, or braay	I IIII CIIII C WIIC	1 1 0 C C G G I C D

Study Procedures	Diet Phase I		Wash out		Diet Phase II			Total #	
Study weeks (days)	1 (1-7)	2 (8-14)	3 (15-21)	4 (22-28)	5 (29-35)	6 (36-42)	7 (43-49)	8 (50-56)	8 (56)
Food pick up	X	X	X			X	X	X	6
Entrée check list return		X	X				X	X	4
Weight	X	X				X	X		4
Waist circumference	X	X				X	X		4
Blood pressure	X	X				X	X		4
Fasting blood samples*	X	X				X	X		4
Mini-pill ingestion		X					X		2
Stool collection/return**			XXX					XXX	up to 6
Diet 24-hr recalls	X	XX					XX		5
Payment			X					X	2

\*Blood will be drawn in the morning after an overnight fast (8 to 10 hours, no food or drink except water and approved medications). The amount drawn on days 1, 14, 36 and 49 will be 12 mL (about 1 tablespoon) for a total of 48 mL over the entire study (about 4 tablespoons).

#### Diet Phase 1

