## 2. Will subjects be randomized? **☒** Yes

- a. Describe the randomization procedures, including the ratio of subjects randomized to each study arm: The study design is a randomized cross-over trial. Each participant will receive both dietary interventions. Block allocation will be used to generate the randomization sequences, stratified by sex. Assignment to a sequence will be based on order of enrollment at time of consent. If a participant withdraws from the trial prior to completion, their randomization sequence will be locked and subsequent enrollees will be assigned to the next available slot in the allocation table. Only the MRU registered dietitian, kitchen staff and a member of the HNRCA Statistical Core Unit not involved in data analysis will be aware of participants' randomization sequence.
- b. *Describe the blinding procedures:* This is a double-blind study. Only the MRU dietitian, kitchen staff and a member of the HNRCA Statistical Core Unit not involved in analysis will be aware participants' randomization sequence. No identifiers will be included on intervention food items provided to the participants.
- c. Is there a placebo control arm? No
- 4. *Describe the following concerning pregnancy testing and birth control:* None as study participants will be postmenopausal females and males.
- 5. \(\simega Check to confirm that any amendments to the protocol or informed consent documents will be reviewed and approved by the IRB prior to implementation, unless required to eliminate an apparent immediate hazard to subjects.

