## E.3. Evaluations

Will you perform any laboratory tests for this study?

⊠ Yes

If **Yes**, respond to all of the following:

- 1. List all laboratory tests to be done as part of the study (e.g., hematology, clinical chemistry, urinalysis, pregnancy testing) as follows: No screening laboratory tests will be conducted. Fasting venous blood will be drawn and stool collected at the beginning of the study and the end of each dietary phase for research purposes only.
- 2. Describe laboratory methods to provide for appropriate longitudinal and cross-sectional comparison (e.g., use of consistent laboratory method throughout study, use of single, central laboratory for multi-site studies): N/A
- 3. *If more than one laboratory will be used to perform study tests, specify which evaluations will be done by each laboratory:* Analysis of GI luminal content and stool microbiome will be conducted in the laboratory of [name], Tufts School of Veterinary Medicine, a co-Investigator. Analysis of the blood samples for cardiometabolic risk factors (plasma lipids, lipoproteins, inflammatory factors, markers of glucose homeostasis) and stool and plasma metabolomic profiles will be overseen by [name] in the Nutrition Evaluation and Cardiovascular Nutrition laboratories at the HNRCA.

- 4. □ Check to confirm that laboratory tests that will be performed are in compliance with Clinical Laboratory Improvement Amendments (CLIA) of 1988. All laboratory tests are being performed for research purposes only and test results will not be shared with the study participants or their physicians.

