- 5. If samples will be stored for the purpose of this study, describe the preparation, handling, and storage of specimens, including specific time requirements for processing, required temperatures, aliquots of specimens, where they will be stored, how they will be labeled, and what will happen to the samples after the study is over: GI luminal content and stool samples will be aliquoted and stored at -80°C for microbiota analyses. A portion will be freeze-dried for metabolome analysis. Only samples from participants who have consented to optional banking will be retained for archival. All other samples will be destroyed after analysis. Fasting (8 to 10 hour) blood samples will be drawn (12 mL per visit) at the beginning and end of each diet phase for a total of 48 mL over the study duration. Serum and plasma will be isolated and aliquoted into vials by the staff in the HNRCA Nutrition Evaluation Laboratory, and stored in a -80°C freezer until analyses. Samples will be labeled with the date of collection, along with a unique subject identification number, specimen type and diet phase. After the proposed analysis, any remaining blood samples will be destroyed by the respective laboratories performing the analysis unless participants have consented to optional banking.
- 6. Will biospecimens (including those collected for future unspecified research) be (check all that apply):
  - a. \( \subsection \) Subjected to genetic testing (DNA, RNA sequence data, epigenetic data) (risks of genetic testing must be described in the ICF)
  - b. □ Subjected to genome-wide analysis (must be described in the ICF)
  - c.  $\square$  Genotype and phenotype data will be shared for research purposes (this must be described in the ICF, including with whom this data will be shared)
  - d. 

    Used to create a perpetual cell line immortalized (must be described in the ICF)

    Refer to the NIH's FAQ on Human Subjects Research Human Specimens and Cell

    Lines for additional information.
  - e. □ *None of the above will occur*

E.4. Collection, Storage, and Use of Human Biospecimens for Unspecified Futu	re Research
Will biospecimens be collected and stored for unspecified future research?	

 $\boxtimes$  Yes  $\square$  No

If **Yes**, respond to all of the following:

- 1. Describe the role of biospecimen collection and storage in this study (check one):
  - ☐ Biospecimen collection and storage for unspecified future research is the **primary purpose** of the study

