## **H.3. Statistical Analyses**

1. Describe the statistical analyses that will be performed for this study: Microbiota taxonomic profiles across GI locations will be characterized using standard diversity measures as well as relative abundances of specific taxa. Alpha diversity and beta diversity measures will be compared across regions using repeated measures ANOVA to account for multiple samples from the same individual. Effects of a plant-based and meat diet on GI tract microbiota will be compared, by region, using zero-inflated Gaussian mixed models, implemented in the R package "glmmTMB". These models can include fixed and random effects to account for dependencies from the crossover design, and evaluate sequence and period effects on the microbiota taxonomic profiles. To compare the effect of the of the plant-based and meat diets on cardiometabolic risk factors, absolute values at the end of each diet phase and change from baseline to 2 weeks after randomization will be compared using a two sample t-test or Wilcoxon Rank Sum test.

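### H.3 plans two unranked analyses of each cardiometabolic marker and no regression on the phase baselines, so the precision obtained depends on unknown correlations

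*Protocol*

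**What the plan says.** H.3 gives each cardiometabolic marker two outcomes: "absolute values at the end of each diet phase and change from baseline to 2 weeks after randomization will be compared". It also fixes the test, since both "will be compared using a two sample t-test or Wilcoxon Rank Sum test". It does not say which outcome leads, and it names no baseline covariate. For the microbiota, the same section chooses a richer tool: "These models can include fixed and random effects to account for dependencies from the crossover design".

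The design is a two-period crossover. The randomization item under E.2 states that "Each participant will receive both dietary interventions", and E.2 adds: "There will be a 2-week washout period between the phases".

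On blood samples, the footnote to Table 1 in E.2 says: "The amount drawn on days 1, 14, 36 and 49 will be 12 mL". The Day 36 visit described under Diet Phase II includes a fasting sample, and E.3 item 5 has blood drawn "at the beginning and end of each diet phase for a total of 48 mL over the study duration". E.3 item 1 differs: "Fasting venous blood will be drawn and stool collected at the beginning of the study and the end of each dietary phase". That wording leaves out Day 36.

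The comparison serves the exploratory aim in B.1. H.2 gives no SD, correlation or power for these markers.

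**The concern.** Two analyses of one marker can disagree, and H.3 has no rule for which is read. Each also fixes in advance how far the baseline counts. The end value gives it weight 0 and the change score gives it weight 1. In a crossover, where each participant already serves as their own control, subtracting a phase baseline can add more noise than it removes; ignoring an informative baseline wastes it. A fitted slope takes the weight from the data. Four draws per participant are scheduled, so the information is already being collected. What is at stake is precision, and a single clear reading, for the exploratory aim.

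**Working it through.** **Inputs from the protocol.** Draws on Days 1, 14, 36 and 49 (E.2); 30 completers (H.2). The protocol states no precision figure for these markers, so there is none to reproduce. The blood volume does reproduce, 4 × 12 = 48 mL, and it agrees with four draws.

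**Assumptions.** The four values have equal variance s². The correlation is rw between baseline and end within a phase, and rb between any two values from different phases. Completers split 15 per sequence. Comparisons are made within participants and use both phase baselines.

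**Formulas.** Let dY be a participant's difference in end values between phases and dB the difference in baselines.

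- Var(dY) = Var(dB) = 2s²(1 − rb), and Cov(dY, dB) = 2s²(rw − rb).
- The correlation of dY with dB, which is also the slope, is k = (rw − rb)/(1 − rb).
- End value: 2s²(1 − rb).
- Change: Var(dY − dB) = 4s²(1 − rw).
- Adjusted: 2s²(1 − rb)(1 − k²).
- Since 1 − k = (1 − rw)/(1 − rb), change ÷ adjusted = 2/(1 + k) and end ÷ adjusted = 1/(1 − k²).

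Neither ratio can fall below 1. Change beats the end value only if k > 0.5, that is, rw > (1 + rb)/2.

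**Cost of estimating the slope.** With 30 completers in two sequences, the adjusted variance is multiplied by 1 + 1/(30 − 4) = 1.038.

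**Numbers for assumed rb = 0.7 (variances in units of s²).**

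| rw | k | End | Change | Adjusted | Change ÷ adj. | End ÷ adj. | Adj. at n = 30 | Better planned ÷ adj., n = 30 |
|---|---|---|---|---|---|---|---|---|
| 0.75 | 0.167 | 0.60 | 1.00 | 0.583 | 1.71 | 1.03 | 0.606 | 0.99 |
| 0.80 | 0.333 | 0.60 | 0.80 | 0.533 | 1.50 | 1.125 | 0.554 | 1.08 |
| 0.85 | 0.500 | 0.60 | 0.60 | 0.450 | 1.33 | 1.33 | 0.467 | 1.28 |
| 0.90 | 0.667 | 0.60 | 0.40 | 0.333 | 1.20 | 1.80 | 0.346 | 1.16 |

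Over rb 0.5 to 0.8 and rw from rb to 0.9, the large-sample ratios run from 1.1 to 2.0 for change and from 1.0 to 2.8 for the end value.

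**Limits of the gain.** Against the better planned analysis, the ratio peaks at k = 0.5: 1/(1 − 0.25) = 1.33, or 1.33/1.038 ≈ 1.28 with 30 completers. Adjustment loses to the end value when k² < 1 − 1/1.038, that is, |k| below about 0.19. It loses to change when (1 + k) × 1.038 > 2, that is, k above about 0.93. The loss is at most about 4%, or 30 × 0.038 ≈ 1 participant.

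**Simulation check (20,000 crossover trials, 15 + 15, rb = 0.7).** End : change : adjusted came out as 1 : 2.00 : 1.04 at rw 0.70, 1 : 1.32 : 0.92 at 0.80, 1 : 0.99 : 0.77 at 0.85 and 1 : 0.68 : 0.58 at 0.90, in line with the formulas.

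**Two unranked tests.** The two estimates have correlation √((1 − k)/2). If each test were valid at 0.05, the chance under the null that at least one rejects would be about 0.083 at k = 0 and 0.096 at k = 0.9, per marker.

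**The case against.** The strongest reply is that end values and changes are often reported side by side, that no confirmatory claim rests on either, and that an SAP, which is not shown, may name the lead outcome. That stands as a reason for low severity. It does not remove the point, because H.3 itself names both outcomes and the tests.

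Four stronger readings are tempting, and the documents do not support them.

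- A reader might infer that 30 completers are worth only 17 to 20 (30/1.71 and 30/1.50). That sets adjustment against the change score alone. H.3 also plans the end value; against it, in the same two cases, the equivalents are 30 × 0.606/0.60 ≈ 30 and 30 × 0.554/0.60 ≈ 28.
- A reader might infer that adjustment is always at least as precise. That holds in large samples only. With 30 completers it fails at rw 0.75 in the table. If all four values are equally correlated (k = 0), it gains nothing over the end value and costs about 4%.
- A reader might infer that the plan ignores baseline altogether. The change score does use it, with slope fixed at 1; what is absent is regression adjustment.
- A reader might take the ratios as describing the tests as written. They do not. A two-sample test treats one person's two diet values as independent, and the change, read literally, covers Day 1 to Day 14 only. Both are separate faults that must be repaired before these formulas apply.

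Two further reservations stand. The variance ordering is for least squares and has not been shown for the rank test that H.3 also allows. And if a Phase I effect persisted to Day 36 despite the washout, the change score would carry that baseline shift with weight 1 and the adjusted analysis with weight k.

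**Conclusion.** The point holds as a modest matter of efficiency and clarity. H.3 leaves two unranked analyses per marker, and which is imprecise cannot be known beforehand. With rb 0.7 and rw 0.75 to 0.90, both assumed, the change score has 1.7 to 1.2 times the adjusted variance and the end value 1.03 to 1.8 times. The value of adjustment lies mainly in protection against relying on the worse analysis. This rests on within-participant comparison, use of both phase baselines, the equal-variance correlation pattern above, and a washout long enough for Day 36 to serve as a baseline. Severity is low because the aim is exploratory.

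**What to change.** In H.3, name one lead analysis per cardiometabolic marker: the end-of-phase value in a crossover model with participant, period and diet, with the phase baseline (Day 1, Day 36) entered as its within-participant deviation, and skewed markers analysed on a log scale. Report the change score as descriptive only. This is best done in the same edit that replaces the two-sample tests, since the model supplies the pairing. Reconcile E.3 item 1 with E.2 and E.3 item 5 on the Day 36 draw, because the covariate depends on it.

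The cost is a sentence or two in H.3 and one in E.3, plus one degree of freedom. Beyond the four draws that E.2 already schedules, no samples are needed.

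### Read literally, the cardiometabolic change score covers Phase I only, so this one outcome is compared between persons and the Day 36 blood enters no stated analysis

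*Protocol*

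**What the plan says.** One sentence of Protocol H.3 names two cardiometabolic outcomes. The first is "absolute values at the end of each diet phase". The second is "change from baseline to 2 weeks after randomization will be compared using a two sample t-test or Wilcoxon Rank Sum test". The two tests named there serve both outcomes. In the same section, sequence and period effects are mentioned only for the microbiota models.

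On the design, E.2 item 2a says: "Each participant will receive both dietary interventions". On timing it says: "Assignment to a sequence will be based on order of enrollment at time of consent". The day-by-day schedule in E.2 has the study consent signed on Day 1. No second randomization is described.

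On blood sampling, the footnote to Table 1 in E.2 says: "The amount drawn on days 1, 14, 36 and 49 will be 12 mL". E.3 item 5 agrees: "Fasting (8 to 10 hour) blood samples will be drawn (12 mL per visit) at the beginning and end of each diet phase". E.3 item 1 does not: it lists blood at the start of the study and at the end of each phase, which leaves out Day 36.

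B.1 makes the comparison of blood biomarkers an exploratory aim, and H.1 does not list these markers among the endpoints.

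**The concern.** A crossover lets each person serve as their own control. A change score tied to the single act of randomization cannot exist in Phase II, because nobody is randomized at Day 36. Applied as written, the change comparison sets those who ate meat entrées first against those who ate plant-based entrées first, on Phase I data alone. The start-of-phase draw in Phase II, which would supply the second change and show whether markers had returned to their starting level after washout, has no stated use. At stake is the precision of one exploratory comparison, together with the risk that the change score is settled only once results are visible.

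**Working it through.** The protocol gives no sample size or power for the cardiometabolic markers, so there is no stated figure to reproduce. The check compares the literal definition with what the scheduled bloods allow.

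**Which draws each outcome uses**

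| Outcome | Day 1 | Day 14 | Day 36 | Day 49 |
|---|---|---|---|---|
| End-of-phase values (H.3) | no | yes | no | yes |
| Change score as worded (H.3) | yes | yes | no | no |
| Change defined within each phase | yes | yes | yes | yes |

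**Inputs.** There are 30 completers (H.2). A 1:1 split by sequence, 15 and 15, is assumed: the protocol's 15 and 15 are men and women, and E.2 item 2a gives no sequence ratio. Let s be the SD of a two-week change and r the correlation between a person's two phase changes. The protocol gives neither.

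**Literal definition, two-sample.** SE = s√(1/15 + 1/15) = s√(2/15) = 0.365s.

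**Both phases, within person.** SE = s√(2(1 − r)/30). At r = 0 this is s√(2/30) = 0.258s.

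**Ratio at r = 0.** 0.365/0.258 = √2 = 1.41, so the variance is doubled.

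**Is r = 0 a fair reference?** The two changes share no measurement. If a person's four values are equally correlated (ρ), the correlation of the two changes is proportional to ρ − ρ − ρ + ρ = 0. A positive r needs something more, such as individuals who respond in the same direction on either diet. The ratio is √(2/(1 − r)): 1.69 at r = 0.3 and 2.00 at r = 0.5. Nothing in the protocol supports those values of r.

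**Non-completers.** C.4 keeps data already collected from people who withdraw, so Phase I may hold more than 15 per sequence. With m per sequence, SE = s√(2/m), and the ratio to 0.258s is √(30/m): 1.41 at m = 15, 1.22 at m = 20, 1.00 at m = 30. The last needs all 60 enrollees to finish Phase I. H.2 counts everyone who signs a screening consent among the 60, so 30 versus 30 is an upper bound.

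**Detectable difference.** Two-sided α = 0.05, 80% power, in SDs of a single value, with equal correlation ρ (assumed):

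| ρ | Phase I change, 15 v 15 | Phase changes within person, n = 30 | End-of-phase values within person, n = 30 |
|---|---|---|---|
| 0.3 | 1.25 | 0.89 | 0.63 |
| 0.5 | 1.06 | 0.75 | 0.53 |
| 0.7 | 0.82 | 0.58 | 0.41 |
| 0.9 | 0.47 | 0.33 | 0.24 |

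In the last column the SE is s/√30 = 0.183s, because s² is then twice the single-value variance times (1 − ρ). Under this pattern, unadjusted phase changes have twice the variance of end-of-phase values, and the literal change score has four times that variance.

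**The other reading.** Suppose H.3 meant two weeks after the start of each phase. Each person then stands in both samples of a test that assumes independent samples. For phase changes the harm depends on r: the unpaired SE stays at 0.258s, while the correct one is 0.258s√(1 − r). For end-of-phase values it is plain. In simulation with 30 pairs and a nominal 5% level, the two-sample t-test rejected a true null in about 0.7% of runs at ρ = 0.5 and 0.1% at ρ = 0.7, so it is very conservative and loses power.

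**The case against.** The best defence is that the wording is loose. Blood is scheduled at the start of both phases, so the authors probably had a change in each phase in mind, and an analysis plan could say so. The other outcome in the sentence already uses both phases, and the aim is exploratory. The low stakes stand. The rest does not remove the need to correct the text: the protocol states a definition, that definition fits only Phase I, and under the charitable reading the named tests are still unpaired.

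Three stronger inferences are tempting and are not supported.

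- A reader might infer that Day 49 is discarded, or that the whole cardiometabolic analysis becomes parallel. It does not: end-of-phase values use Day 14 and Day 49. Only Day 36 has no stated use.
- A reader might take 15 versus 15 by sequence as the protocol's figure. It is an assumption, and retained Phase I data could raise it.
- A reader might infer an interval up to twice as wide. That needs r = 0.5, for which the protocol offers no basis.

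The absence of a stated washout check is also no fault in itself, since an analysis plan not shown here may hold it.

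**Conclusion.** The point holds for the change outcome alone. As written, it is a Day 1 to Day 14 comparison between persons, although the design supplies a change under each diet for each completer. Its standard error is about 1.41 times that of a within-person comparison of phase changes, given 30 completers, an even split by sequence and uncorrelated changes. The loss shrinks towards none as non-completers' Phase I data are added, and grows only with a positive correlation between a person's two changes. This should be corrected before analysis, but it does not touch the microbiota endpoints or the sample size.

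**What to change.** In H.3, define change within each phase: Day 14 minus Day 1, and Day 49 minus Day 36. Replace the two-sample t-test and rank sum test with a within-person analysis: paired, or a mixed model with diet, period and sequence. Redefining the change without replacing the test is not enough. A mixed model can also keep the Phase I data of people who withdraw.

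An alternative is to model end-of-phase values within person with the phase baseline as covariate. This is a different estimator, not a restatement of the change score, and the choice should be deliberate because unadjusted phase changes can be less precise than end-of-phase values.

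The Phase I comparison can stay as a sensitivity analysis for carry-over, and Day 36 against Day 1 by sequence can serve as a washout check.

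Reconcile E.3 item 1 with E.2 Table 1 and E.3 item 5 on whether blood is drawn at the start of Phase II. If it is, as the latter two state, the cost is wording only: all four draws are already scheduled.

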#### Exploratory aim:

To compare the effects of diets containing meat and plant-based meat alternatives on metabolites in stool and blood biomarkers associated with cardiometabolic risk.

The ingestible mini-pill is a non-invasive, single-use, passive collection device that is not intended for diagnosis or treatment. The mini-pills have already been developed, tested and validated by two Tufts researchers, Drs. [name] (School of Engineering) and [name] (School of Veterinary Medicine), *in vitro*, *ex vitro*, and *in vivo* in animal models (*Supplement 1: Research Strategy and Supplement 2: Soft Autonomous Ingestible Device for Sampling the Small Intestinal Microbiome, Del-Rio-Ruiz R et al.*, *manuscript in review*). A NSR device designation is being sought from the IRB to conduct a 2-phase randomized-controlled double blind crossover trial in humans by providing two entrées per day containing either meat or plant-based meat alternatives for up to 3 weeks each. After 2 weeks on each diet, participants will consume a provided breakfast meal and then be asked to swallow 6 mini-pills along with a blue food coloring dissolved in 50 mL of water, return home and collect stool samples until all the mini-pills are recovered (varies between 2 and 4 days, but can be up to 6 days). This protocol will allow us to describe the diet-induced progressive change in the GI tract microbiota prior to and including that in the stool.

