#### **H. Statistical Considerations**

#### **H.1. Study Endpoints**

- 1. Describe the primary and secondary study endpoints: GI luminal content and stool microbial composition.
- 2. Describe any primary or secondary safety endpoints: Recovery of the 12 mini-pills.

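### Exploratory cardiometabolic end-of-phase values come from the same people under both diets but are compared with tests for independent groups

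*Protocol*

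**What the plan says.** Section H.3 (Statistical Analyses) names two quantities for the cardiometabolic risk factors: "absolute values at the end of each diet phase" and "change from baseline to 2 weeks after randomization". Both "will be compared using a two sample t-test or Wilcoxon Rank Sum test".

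Section E.2, item 2a (randomization), describes a randomized crossover: "Each participant will receive both dietary interventions". Table 1 in E.2 schedules fasting blood on Days 1, 14, 36 and 49, so each completer has a value at the end of each diet.

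For the microbiota, the same H.3 paragraph uses repeated measures ANOVA and mixed models. Of the latter it says: "These models can include fixed and random effects to account for dependencies from the crossover design", and it adds that sequence and period effects can be evaluated. Nothing comparable is named for the blood biomarkers.

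These biomarkers belong to the exploratory aim in B.1: "To compare the effects of diets containing meat and plant-based meat alternatives on metabolites in stool and blood biomarkers associated with cardiometabolic risk". The primary and secondary endpoints in H.1 are "GI luminal content and stool microbial composition", so the point does not touch them.

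**The concern.** A two-sample t-test and a rank-sum test both assume that the two sets of values come from different people. Here they come from the same people. Differences between participants in lipids, glucose or inflammatory markers cancel out of a within-person comparison, but they stay in the error term of an unpaired test. The named tests also ignore period.

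At stake is sensitivity. Small to moderate diet effects could be missed although the paired data needed to detect them are collected. A null result from a test whose real size is well below 5% could also be misread as evidence of no difference.

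A secondary point of wording concerns the change score. Under E.2 item 2a, "Assignment to a sequence will be based on order of enrollment at time of consent", so sequence is assigned once. The change score then most naturally means Day 1 to Day 14, that is, Phase I only. On that reading the diets are in different people and an unpaired test is valid and free of carryover. The text does not say whether leaving out the Phase II change is intended.

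**Working it through.** **Inputs.** 30 completers (H.2). Two-sided alpha 0.05: H.2 gives 0.05 for the microbiota calculation, and two-sidedness is assumed. The protocol states no power, SD, effect size or correlation for these outcomes, so there is no figure of its own to reproduce. I assume rho of 0.3, 0.5, 0.7 and 0.9, and express effects in between-person SD.

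**Standard error.** The true variance of the mean difference is 2(1-rho)/30, whereas the two-sample test uses 2/30. The ratio of standard errors is 1/sqrt(1-rho). At rho = 0.5 this is sqrt(0.0667)/sqrt(0.0333) = 0.258/0.183 = 1.41.

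**Size and power.** Type I error and power come from simulated bivariate normal pairs. The crossover analysis is a t-test of within-person period differences between the two sequences, 15 and 15, on 30 - 2 = 28 df. Its detectable differences come from the noncentral t with variance 2(1-rho)/30.

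| | rho 0.3 | rho 0.5 | rho 0.7 | rho 0.9 |
|---|---|---|---|---|
| SE overstated by | 1.20 | 1.41 | 1.83 | 3.16 |
| Type I error, two-sample t | 2.0% | 0.7% | 0.1% | ~0% |
| Power at 0.4 SD, two-sample t | 30% | 27% | 23% | 14% |
| Power at 0.4 SD, crossover with period | 43% | 56% | 78% | 99.7% |
| Power at 0.4 SD, rank-sum as written | 28% | 25% | 22% | 15% |
| Power at 0.4 SD, rank-sum on period differences by sequence | 40% | 52% | 74% | 99.4% |
| Power at 0.8 SD, two-sample t | 90% | 93% | 97% | 99.7% |
| Power at 0.8 SD, crossover with period | 95% | 99% | ~100% | ~100% |
| Difference detectable with 80% power, two-sample t | 0.70 SD | 0.67 SD | 0.64 SD | 0.60 SD |
| Difference detectable with 80% power, crossover with period | 0.63 SD | 0.53 SD | 0.41 SD | 0.24 SD |

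**Unequal sequences.** Under E.2 item 2a a withdrawn participant's slot is locked, so completers need not split evenly by sequence. At 20/10 the crossover power at 0.4 SD is 39 / 51 / 73 / 99.4% across the four values of rho, still well above the unpaired test. A paired test without a period term then absorbs (20 - 10)/30 = one third of any period effect. For an assumed period effect of 0.3 SD that is 0.10 SD, and its type I error is about 7% at rho 0.5 and 8% at rho 0.7. With the period term it stays at 5%. At 18/12 the share is 6/30 = one fifth, or 0.06 SD, and the paired test stays at about 5%.

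**Change score (secondary).** I assume all four draws are equally correlated. With m participants per group, the Phase I change has variance 4(1-rho)/m. Using both phases in 30 completers gives 4(1-rho)/30. At rho 0.5 the detectable difference is 1.06, 0.91 and 0.81 SD for m = 15, 20 and 25, against 0.75 SD with both phases. The protocol does not say how many will reach Day 14, and C.4 keeps the data of those who withdraw. The gap could therefore be as large as 1.06 - 0.75 = 0.31 SD or as small as 0.81 - 0.75 = 0.06 SD.

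**The case against.** **Weight.** The outcomes are exploratory, the protocol claims no power for them, and under positive correlation the error is conservative. At 0.8 SD the test as written already has at least 90% power. The size of the loss rests on an assumed rho and effect. All of this stands and limits the weight of the point, but it does not make the named tests right.

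**A two-sample test can be valid in a crossover** if applied to within-person period differences between sequences. H.3 does not say this: it compares absolute end-of-phase values and mentions neither period differences nor sequence for these outcomes.

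**A separate analysis plan may refine the method.** It may, but the protocol has not left the choice open. It names tests that do not fit its own design.

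**A plain paired test would be enough.** This is largely fair. If sequences start balanced and dropout is unrelated to sequence, a split of 20/10 or worse among 30 completers has a probability of 0.04%, 0.9% or 1.9% with 40, 50 or 60 randomized. So 20/10 is a stress case, and a paired test would already recover most of the loss. The mixed model is still preferable: it covers the unlikely case at almost no cost and matches the approach H.3 already takes for the microbiota.

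**The change score is not an error** if it means Phase I only. Agreed; the request there is only for clarity.

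**Conclusion.** The concern holds. For end-of-phase cardiometabolic values, the protocol names independent-groups tests for paired data. With 30 completers and positive within-person correlation, the standard error is overstated by 1.20 to 3.16 times over rho 0.3 to 0.9. Power for a 0.4 SD difference is 14 to 30%, where a crossover analysis would have 43 to 99.7%. The loss is mild at rho 0.3 and large from rho 0.7. Large effects would mostly still be found.

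With balanced sequences there is no excess of false positives. Even at 20/10 with an assumed 0.3 SD period effect, the unpaired type I error stays below 5% (3.1% at rho 0.3, lower above that). It reaches 5.2% only at rho 0.3 with a 0.5 SD period effect.

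These figures rest on the assumed rho and effect sizes and on normal data. The direction of the error needs only a positive within-person correlation. The point should be corrected before analysis, but it does not affect the two specific aims or the H.1 endpoints.

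**What to change.** Replace the sentence in H.3 with, for example: *For the exploratory cardiometabolic outcomes, Day 14 and Day 49 values will be compared between diets with a linear mixed model having diet, period and sequence as fixed effects and participant as a random effect. If a rank-based method is needed, within-person period differences will be compared between the two sequence groups with the Wilcoxon rank-sum test.* State in advance what triggers the rank-based method.

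For the change score, say which is meant: Phase I only, labelled as a parallel-group comparison, or each phase (Day 14 minus Day 1, Day 49 minus Day 36) in the same mixed model. Before choosing the second, reconcile the blood-draw schedule. E.3 item 1 lists blood at the start of the study and the end of each phase. Table 1, the Day 36 visit in E.2 and E.3 item 5 also include the start of Phase II.

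The cost is one or two sentences before analysis, and 28 residual degrees of freedom instead of 58. The end-of-phase correction needs no new samples, because the Day 14 and Day 49 draws are planned under every description. Only a per-phase change score depends on the Day 36 draw.
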